3.2 Sample Size

Approximately 20 subjects will be enrolled in this study.

3.3 Adaptive Design

The rules for halting enrollment are based on an mTPI design. The mTPI models the probability of toxicity for each dose level using a Bayesian model where each dose level has the same prior on the probability of toxicity, a Beta (1,1). When subjects are treated at the current dose level, the posterior probability of toxicity is updated using the observed data from this level. Enrollment recommendations are made based on this posterior probability of toxicity, using three toxicity probability intervals (TPI).

- Under-dosing TPI: DLT rate from 0 to < 20%
- Target TPI: DLT rate from 20% to 33%
- Over-dosing TPI: DLT rate > 33%

For the current dose level and after adjusting for the width of each TPI interval, if the DLT rate is most likely in the under-dosing TPI or most likely in the target TPI then the recommendation is to continue enrollment at the current level. If the DLT rate is most likely in the over-dosing TPI then the recommendation is to halt enrollment.

4. Covariates and Subgroups

4.1 Planned Covariates

There are no planned covariates in this study.

4.2 Subgroups

The baseline variables for the subgroup analyses may include:

- baseline demographics and characteristics:
 - age (< 65, 65-74, ≥ 75 years)
 - sex (female, male)
 - race (White, Asian, other)
- baseline disease characteristics:
 - revised International Staging System (ISS) stage (Stage I, Stages II or III)
 - BM percent of plasma cells (< 50%, ≥ 50%)
 - 
 - extramedullary disease (yes, no). Until safety evaluation is complete for 3 subjects with EM disease, imaging evaluation at screening will be used to document EM disease status.
- number of prior lines of therapy (only 3, > 3)

- prior allogeneic HSCT (yes, no)
- refractory to
 - IMiD (yes, no)
 - PI (yes, no)
 - IMiD + PI (yes, no)
 - daratumumab or other CD 38-targeting antibody (yes, no)

Subgroup analysis will not be performed due to each sub group may not have justifiable count as less number of sample size.

5. Definitions

Adverse Event (AE)

An adverse event is defined as any untoward medical occurrence in a clinical trial subject. The event does not necessarily have a causal relationship with study treatment. The definition of adverse events includes worsening of a preexisting medical condition. A preexisting condition that has not worsened during the study, or involves an intervention, is not considered an adverse event.

Age at Enrollment

Subject age at enrollment will be determined using the age in years reported in the clinical database.

Baseline

For any variable, unless otherwise specified the baseline is the last assessment taken prior to the first administration of AMG 420. For parameters/assessments not scheduled to be performed (or scheduled but not performed) on the same day as the first administration of AMG 420, the baseline value is the value from the screening period measured closest to the day of first administration of AMG 420.

Baseline ECG Values in Triplicate

For the three sets of triplicate pre-dose ECG, the mean of values in a triplicate should be calculated before taking the mean of the three sets of averages. For all post-baseline ECG, the mean value for measurements taken at the same assessment will be calculated and used in the analysis. When an ECG is missing within a triplicate, all available data will be averaged for that time point.

Death Date

For subjects who die during the study, the death date will be recorded on the end of study CRF in the date subject ended study field. Incomplete death dates where only the day of death date is missing will be imputed using the following rules:

Day 1 of the month will be used if year and month indicate that death happened in different month from last known alive date;

One day after last known alive date will be used if death happened in the same month as last known alive date.

The imputed death date will be used in calculation of duration of response, progression-free survival and overall survival.

Dose-limiting Toxicities (DLTs)

Investigators determine whether a TEAE qualifies as a DLT per the definition described in protocol Section 7.4.1. For an adverse event to qualify as a DLT, the start date must be within 28 days from the date of the first dose of investigational product.

Best Overall Response

Best overall response for a subject is the best observed post baseline disease response per the International Myeloma Working Group Uniform Response Criteria for Multiple Myeloma (IMWG-URC). **The detailed algorithm is provided in [Appendix B](#).**

Overall Response Rate (ORR)

ORR refers to the proportion of subjects with an objective response. Objective response refers to any of the following responses per the International Myeloma Working Group Uniform Response Criteria for Multiple Myeloma (IMWG-URC): (sCR, CR, VGPR or PR) Per IMWG-URC, any response requires 2 consecutive assessments made any time before starting any new therapy. Subjects who do not experience a sCR/CR/VGPR/PR or do not have any follow-up tumor assessments will be regarded as non-responders.

Duration of Response (DOR)

Duration of response (DOR) will be calculated for subjects who achieve a PR or better. For such subjects, the duration of overall response is defined as the time (months) from first documentation of response to disease progression or death due to any cause. Dates of progression and censoring will be determined as described for the analysis of PFS.

DOR (in months) = (Earliest date of disease progression, death, censor - Date of first observation of PR or better before confirmation + 1)/30.4

Subjects who have not ended their response at the time of analysis will have DOR censored on the date of their latest evaluable assessment.

Time to response

Time to response applies for subjects who achieved best overall response of PR, VGPR, CR or sCR. Time to response is calculated as the number of months (one month = 30.4 days) from the first administration of AMG 420 to the first objective assessment of response (ie, date of the first detection of response) as per IMWG-URC.

TTR (in months) = (Date of objective response – Date of first dose + 1)/30.4

MRD Negativity (MRD-)

MRD- is defined as a response of CR or sCR accompanied by any of the following types of MRD negativity.

- Sustained MRD-
- Sequencing MRD-
- Imaging plus MRD-

Subjects who do not experience a MRD negativity or do not have any evaluable follow-up assessments will be regarded as MRD non-responders.

Progression-free survival (PFS)

Progression free survival (PFS) is defined as number of months between start of treatment and first evidence of documented disease progression or death (due to any cause), whichever occurs first.

PFS (in months) = (Earliest date of disease progression, death, censor – Date of first dose + 1)/30.4

Progression-free survival will be right-censored for subjects who meet one of the following conditions: 1) no post baseline disease assessments, 2) non-protocol systemic anticancer treatment started before documentation of PD or death, 3) death or disease progression after more than 1 missed disease assessment visit or 4) alive and does not have documentation of PD before a data analysis cutoff date. For such subjects, the

primary analysis of PFS will be right-censored according to the conventions described in [Table 2](#).

Table 2. Conventions for Censoring for PFS and DOR

Situation	Date of Progression or Censoring	Outcome
No post baseline disease assessments**	Date of first dose	Censored
New anticancer therapy started before documentation of PD or death	Date of last evaluable disease assessment prior to start of new anticancer therapy	Censored
Death or PD immediately after more than 1 consecutively missed disease assessment visit*	Date of last evaluable disease assessment visit before the first missed visit	Censored
Alive and without PD documentation (including lost to follow-up without PD)	Date of last evaluable disease assessment	Censored
Death or PD between planned disease assessments	Date of death or first disease assessment showing PD, whichever occurs first	Progressed
Death before first disease assessment	Date of death	Progressed

* If death or PD is more than 84 days after previous disease assessment, or Study Day 1 if there is no previous disease assessment.

** Only apply to PFS.

Overall survival (OS)

Overall survival is defined as the interval from Study Day 1 until death due to any cause; otherwise, OS is censored on the last recorded date on which the subject was alive.

Last Evaluable Disease Assessment Date

For responses assessed by investigator, last disease assessment date is the last evaluable response assessment date collected using IMWG Response CRF (except the response assessment date of Inevaluable) before confirmed PD, on or before new anti-cancer therapies or procedures.

Last Known Alive Date

For subjects not known to have died, their last date known to be alive will be determined as the latest date associated with clinic visits before data cutoff date including, for example, but not limited to the following:

- Date of Enrollment on Subject Enrollment CRF
- Date First Taken, Date Last Taken on Concomitant Medications CRF

- Date Performed on ECOG Performance Status, Vital Signs, Electrocardiogram, Procedures CRFs
- Admission Date, Discharge Date on Hospitalizations CRF
- Date of Examination on Physical Measurement CRF
- Date Collected on Reproductive Status and Pregnancy Test (Local Lab), Chemistry (Local Lab), Hematology (Local Lab), Coagulation (Local Lab), Urinalysis (local Lab), Immunology (Local lab) CRFs and in central lab data
- Date of Assessment on IMWG Response for Time Point, Peripheral Neuropathy Assessment CRFs
- Start Date and End Date on Investigational Product Administration CRF
- Date Started and Date Ended or Resulted in Death on Events CRF
- Start date, Stop date on Anti-Myeloma / Anti-Cancer Therapies, Other Protocol Required Therapy (GLUCOCORTICOID), Other Protocol Required Therapy (Tocilizumad), Hematopoietic Stem Cell Transplantation Autologous, Hematopoietic Stem Cell Transplantation Allogenic CRFs
- Subject Status Date if status is Alive on Survival Status CRF
- Assessment Date on Skeletal Survey and Plasmacytoma Assessment CRF
- **End_of study date if the subject's primary reason for ending study is not "Lost to follow-up"**

Fridericia-corrected QT Interval (QTcF)

The Fridericia correction will be calculated from the investigator reported QT (msec) and RR interval (msec), as follows:

$$QTcF = QT / (RR/1000)^{1/3}$$

Change From Baseline

Change from Baseline is the arithmetic difference between post-dose assessments and Baseline value.

Change (absolute) from Baseline = (Post-baseline Value – Baseline Value)

Change (percent) from Baseline

$$= [(Post-baseline Value – Baseline Value) / Baseline Value] \times 100$$

Investigational Product (IP)

The term 'investigational product' is used in reference to AMG 420.

Primary Completion:

The primary completion date is defined as the date when the last subject is assessed or receives an intervention for the final collection of data for the primary endpoint(s), for the

purposes of conducting the primary analysis, whether the study concluded as planned in the protocol or was terminated early.

If the study concludes prior to the primary completion date originally planned in the protocol (ie, early termination of the study), then the primary completion will be the date when the last subject is assessed or receives an intervention for evaluation in the study (ie, last subject last visit).

End of Study

The end of study (EOS) date is defined as the date when the last subject across all sites is assessed or receives an intervention for evaluation in the study (ie, last subject last visit), following any additional parts in the study (eg, LTFU), as applicable.

Lost to Follow-up

A subject will be considered lost to follow-up if he or she repeatedly fails to return for scheduled visits and is unable to be contacted by the study site. The following actions must be taken if a subject fails to return to the clinic for a required study visit:

- The site must attempt to contact the subject and reschedule the missed visit as soon as possible and counsel the subject on the importance of maintaining the assigned visit schedule and ascertain whether or not the subject wishes to and/or is able to continue in the study.
- In cases in which the subject is deemed lost to follow-up, the investigator or designee must make every effort to regain contact with the subject (where possible, 3 telephone calls and, if necessary, a certified letter to the subject's last known mailing address or local equivalent methods). These contact attempts are to be documented in the subject's medical record.
- If the subject continues to be unreachable, he/she will be considered to have withdrawn from the study with a primary reason of lost to follow-up.
- For subjects who are lost to follow-up, the investigator can search publicly available records where permitted to ascertain survival status. This ensures that the data set(s) produced as an outcome of the study is/are as comprehensive as possible.

Study Day

Post study day: study day= (date - date of Study Day 1) + 1

Pre study day: study day= (date – date of Study Day 1)

Study Day 1

It is defined as the first day that protocol-specified investigational product is administered to the subject.

Treatment-emergent Adverse Event (TEAE)

A treatment-emergent adverse event is any adverse event starting on or after the first administration of investigational product, as determined by the flag indicating if the adverse event started prior to the first dose on the Events CRF, and up to and including 33 days after the last IP dose date or EOS date, whichever occurs first. The severity of each adverse event will be graded using the CTCAE version 5.0 with exception of CRS which will be graded according to adopted grading system in Lee et al, 2014 and TLS that will be graded according to Cairo-Bishop criteria (refer to protocol Appendix 12). Adverse events will be coded using MedDRA.

Safety Follow-up

SFU visit will be conducted 30 (+3) days after last administration of AMG 420.

Long-term Follow-up

LTFU period begin after the SFU visit is completed. The total duration of the LTFU will be up to 5 years from the first dose of AMG 420, or until subject death, whichever is first."

6. Analysis Sets

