**Table 2-2. Phase 1b Treatment Cycle 2, 3, and Following to End of Study**

Cycle	Treatment Period													Follow-up Period			
	2						Infusion-free Interval a	3 and all subsequent cycles					Infusion-free Interval a	EOT	SFU	LTFU b,v	
Cycle Day	1	2	8	15	22	29	36	1	8	15	22	29	36		30 (+3) days	Up to 5 yrs after first dose of IP, or subject death, whichever occurs first	
Hours	Pre-dose	Relative to start of infusion						Pre-dose	Relative to start of infusion								
		6	24					4									
BIOMARKER ASSESSMENTS (continued)																	
INVESTIGATIONAL PRODUCT DOSING																	
AMG 420 cIV infusion	----->							----->									
Premedication t	X							X									

Footnotes defined on next page

AE = adverse event; [REDACTED]; cIV = continuous intravenous; CR = complete response; CRS = cytokine release syndrome; CT = computed tomography; [REDACTED] ECG = electrocardiogram; ECOG = Eastern Cooperative Oncology Group; EOI = end of infusion; EOT = end of treatment; EOS = end of study; Ig = immunoglobulins; IP = investigational product; LTFU = long-term follow-up; MDSCs = myeloid derived suppressor cells; MM = multiple myeloma; MRD = minimal residual disease; MRI = magnetic resonance imaging; [REDACTED] PB = peripheral blood; PD = progressive disease; PET = positron emission tomography; [REDACTED]; PK = pharmacokinetics; PR = partial response; SAE = serious adverse event; [REDACTED]; [REDACTED]; sFLC ( $\kappa/\lambda$ ) = serum free light chain (kappa/lambda); SFU = safety follow-up; SIFE = serum immunofixation; SPEP = serum protein electrophoresis; UIFE = urine immunofixation; UPEP = urine protein electrophoresis

a Infusion-free interval = days 30 to 42, day 43 = day 1 of subsequent cycle. In case of extended treatment-free interval (treatment holiday), an on-site visit should be performed within one week prior to re-start of study treatment, assessments will be performed as on day 36 of cycle 1 (see [Schedule of Assessment Table 2-1](#)).

b LTFU via on-site visit every 6 weeks ( $\pm 7$  days) until progression of disease. Afterwards, LTFU frequency will be 3 months for collecting information on survival and subsequent anti-MM treatment only, without the requirement for on-site visits.

c See [Section 7.1.1.4.1](#) for details on hospitalization requirements.

d See [Sections 9.2.3.1](#) and [12.4](#) for SAE reporting requirements during LTFU.

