#### **9.1.2 Treatment Period**

Visits will occur per the Schedule of Activities ([Section 2.2](#)). The date of the first dose of investigational product is defined as day 1. All subsequent doses and study visits will be scheduled based on the day 1 date. Administration of AMG 420 is to be administered as applicable during each visit that it is required.

Starting with day 4 post infusion, assessments should be performed on the indicated study day, but not at a certain hour of the day. The D6 sample may also be taken on D7 if logistically required (eg, sample cannot be processed at the weekend). Bone marrow assessments post-treatment start may be performed within a window of  $\pm 3$  days. Visits during treatment-free interval, if applicable, may occur within a window of  $\pm 1$  day.

Furthermore, start of a treatment cycle can be delayed for administrative/logistical reasons for up to 7 days to allow for appropriate scheduling. **Start of treatment cycles later than 7 days from planned next cycle day 1 must only occur** after discussion with and final approval by sponsor. **Delays of treatment cycles beyond 14 days are not permitted.**

The DLRT may implement a  $\pm$  1-day window for infusions following the day 1 infusion.

In any case of premature treatment discontinuation prior to day 29 (EOI) the assessments for day 29 do not have to be performed, but the investigator should make every effort to perform all examinations scheduled for the EOT (see [Section 2.2](#)).

The expected treatment period is to treat until PD per IMWG (or other protocol-specific reasons as per [Section 8.1](#)).

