### 9.1.5 Long-term Follow-up

Following the SFU visit, there will be a LTFU period for clinical evaluation of disease status and survival. All subjects will be followed every 3 months ( $\pm$  2 weeks) for survival and anti-multiple myeloma treatment (on-site visits are not required, if needed also interrogation of public databases is acceptable). For subjects who discontinue treatment for reasons other than PD or death, additional on-site visits are required every 6 weeks ( $\pm$  7 days) for assessments of disease status and documentation of anti-multiple

myeloma treatment until PD. Subjects will be followed for a maximum of 5 years from the first dose of AMG 420, or until subject death, whichever occurs first.

Subjects will allow Amgen continued access to medical records so that information related to subjects' health condition, including disease status, response to treatment, and survival, may be obtained.

The procedures that will be performed during the LTFU are designated in the Schedule of Assessments ([Section 2.2](#)) as long as on-site visits apply.

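### The SAP's 84-day footnote censors some progressions found after a single missed visit, which its own PFS and DOR rule counts as events

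*SAP*

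**What the plan says.** SAP Section 5 gives the rule in words and again in Table 2. In words, one of the four PFS censoring conditions is "death or disease progression after more than 1 missed disease assessment visit". The Table 2 row reads "Death or PD immediately after more than 1 consecutively missed disease assessment visit" and censors at the last evaluable assessment before the first missed visit. An asterisk on that row leads to the footnote: "If death or PD is more than 84 days after previous disease assessment, or Study Day 1 if there is no previous disease assessment". Another row, "Death or PD between planned disease assessments", is classed as an event. DOR inherits these dates: "Dates of progression and censoring will be determined as described for the analysis of PFS".

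The protocol sets the schedule:

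- **Follow-up.** Table 2-2, footnote b, has "LTFU via on-site visit every 6 weeks", with a window of ± 7 days, until progression. Section 9.1.5 limits these visits to subjects who stopped treatment for reasons other than progression or death; for them "additional on-site visits are required every 6 weeks", with the same window.
- **Treatment.** From cycle 2, the serum, urine and free light chain panel is drawn on day 1 of each cycle, and the standard cycle is 42 days (Table 2-2). Section 9.1.2 adds that "start of a treatment cycle can be delayed for administrative/logistical reasons for up to 7 days". Longer delays need sponsor approval and may not exceed 14 days.
- **Extended intervals.** Section 7.1.1.3 lets MRD-negative subjects lengthen the treatment-free interval to as much as 4 weeks, and later 8 weeks.

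**The concern.** The rule counts visits and the footnote counts days. The two agree only if every attended visit falls on its nominal date, which the protocol does not require. The SAP does not say which prevails, and the written condition carries no asterisk. Two careful programmers could therefore classify the same protocol-compliant subject differently.

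When the day count is stricter than the visit count, an observed progression is removed as an event and the subject is censored at an earlier negative assessment. DOR is a key secondary endpoint and PFS a secondary one, in about 20 subjects, so a single reclassified subject is visible on the curve. The SAP plans no analysis that would show the estimates under the rule as worded, or with all events counted.

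**Working it through.** **1. The plan's figure.** 2 intervals × 6 weeks × 7 days = 84 days. This reproduces the footnote exactly, with a window of zero. The SAP does not itself state this derivation.

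**2. Progression found at a follow-up visit.** Let *a* be the number of days by which the last attended visit was off its nominal date, and *b* the same for the visit at which progression is found. Each runs from −7 to +7. With *k* missed visits in between:

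gap = (*k* + 1) × 42 + *b* − *a*

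| Missed visits | Gap in days | Rule in words | Footnote (> 84) |
|---|---|---|---|
| 0 | 28 to 56 | event | event |
| 1 | 70 to 98 | event | event up to 84, censored from 85 to 98 |
| 2 | 112 to 140 | censored | censored |

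If the last visit was on time (*a* = 0), one missed visit gives 84 ± 7 = 77 to 91 days, and 7 of those 15 permitted days lie beyond 84. If both visits may use the window, 105 of the 225 whole-day combinations exceed 84. These are counts of calendar days, not expected frequencies.

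Example: a subject is seen 7 days early, misses the next visit and attends the following one 7 days late with progression. The gap is 84 + 7 + 7 = 98 days with one missed visit. The rule gives an event; the footnote censors.

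**3. Where a day count would separate the two.** For progression found at 6-weekly visits, one miss ends at 98 days and two misses begin at 112. Any cut-off from > 98 to > 111 days separates them exactly. A cut-off of > 91 would still censor one-miss gaps of 92 to 98 days, and > 84 cuts through the middle of the one-miss range.

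**4. On treatment, standard cycle.** Suppose one day-1 panel is omitted and not redrawn, and the two cycle starts slip by *d*₁ and *d*₂ days. The gap is 84 + *d*₁ + *d*₂. Delays of 0 to 7 days per cycle give 84 to 98 days; approved delays of up to 14 days give 84 to 112.

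**5. Extended treatment-free intervals.** The maximum cycle lengths are 28 + 28 = 56 days and 28 + 56 = 84 days. Without a panel at the pre-restart visit, one miss gives 2 × 56 = 112 or 2 × 84 = 168 days. With a panel 1 to 7 days before re-start, one missed day-1 panel gives 56 ± 6 = 50 to 62 days (never beyond 84) or 84 ± 6 = 78 to 90 days (sometimes beyond 84). Table 2-2, footnote a, models that visit on cycle 1 day 36. Whether that day carries the disease panel cannot be read reliably from the extracted tables.

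**6. Scale of one reclassified subject.** With little earlier censoring, the Kaplan-Meier estimate moves by about 1/20 = 0.05 for PFS in all subjects, or 1/10 = 0.10 within a dose level of about 10 (Protocol Section 10.4.2.2 reports efficacy by dose level). For DOR it moves by 1/10 = 0.10 to 1/5 = 0.20 if there are 10 to 5 responders, which is an assumption.

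**The case against.** The best defence is that the asterisk makes 84 days the definition of the row. That would settle the programming but not the contradiction: the written PFS condition has no such definition, and the row's own words classify a compliant subject differently.

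The next defence is rarity, and it largely stands. The 6-weekly schedule covers only subjects who stopped for reasons other than progression. Those who start new therapy before progression are censored under a different row. Sites must try to reschedule missed visits (Protocol Section 8.3), so an omitted on-treatment panel that is never redrawn should be uncommon. The planned censoring reasons (SAP Section 9.1) and subject listings (Section 9.5.2.3) would help to identify affected cases, though they give no alternative estimate.

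A reader might infer three stronger things that the documents do not support.

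- **That PFS and DOR are biased upward overall.** Errors can also run the other way. If the last panel was on day 1 of a full infusion, the end-of-treatment visit falls at about day 28 and safety follow-up at 28 + 30 = 58 to 28 + 33 = 61 days; both carry the panel. If both count as assessments, a subject who misses them and dies on days 62 to 84 has two misses but remains an event. No rates are given from which to weigh the two directions.
- **That deaths on days 85 to 91 are always wrongly censored.** After an on-time visit this holds if a visit is missed only once its window closes (84 + 7 = 91). If it is missed on its nominal date, a death on day 85 follows two misses and the footnote agrees with the rule. The SAP does not define a missed visit.
- **That a subject can be censored with no visit missed.** On a maximal 84-day cycle, an assessment one day late would be at day 85. This requires that the pre-restart visit has no disease panel, which is unresolved.

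**Conclusion.** The point holds as a minor inconsistency in the SAP. For progression found in 6-weekly follow-up, the footnote censors gaps of 85 to 98 days after one missed visit, although the stated rule counts them as events, and this carries over to DOR. This rests only on the documents' own interval, window and threshold. The on-treatment version is also real, but needs an omitted panel plus a delayed cycle start. Extended intervals may add cases, depending on what the pre-restart visit includes.

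The number of subjects affected is unknown, because neither document gives missed-visit or delay rates, and is probably small; on standard 6-weekly schedules with no missed visit it is zero. Each such case turns an event into censoring, but the net direction of bias across the trial is not established. Safety is the primary objective, and PFS and DOR are descriptive.

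**What to change.** Revise the Table 2 footnote before database lock:

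- Censor a progression or death only when at least two consecutive scheduled response assessments (cycle day 1 or 6-weekly follow-up, on the subject's actual schedule) were missed.
- Count a visit as missed only after its permitted window or delay has passed.
- Do not count the end-of-treatment and safety follow-up visits as separate missed assessments. They can lie close together: a subject who stops on cycle day 5 has them at about day 4 and days 34 to 37 after the day-1 panel. Counting both would censor a death on day 40 that the present footnote keeps as an event.
- Keep the Study Day 1 anchor for subjects with no previous assessment, and state how the rule ranks against the Table 2 row that counts a death before any assessment as an event.
- State whether the pre-restart visit counts as a disease assessment.

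If a day count is preferred for the 6-week follow-up schedule, any cut-off from > 98 to > 111 days works for progression found at scheduled visits. It does not serve deaths or the extended cycles.

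Add one sensitivity analysis each for PFS and DOR that counts every documented progression and death as an event regardless of missed visits, with the other Table 2 rows unchanged.

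The cost is one footnote, derivation code that uses each subject's planned visits, and one extra Kaplan-Meier output per endpoint. The downside is that some progressions found late after one missed visit are dated at detection, which lengthens PFS and DOR slightly; the sensitivity analysis does not remove that.
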